**c. Calculations of Sample Size:**

**Objective 1:** Each of the four selected sites have no more than 25 health care workers providing HIV care, so we anticipate a maximum total of 100 health care workers equally divided between each intervention arm and the control arm. With  $n=25$  in all arms, assuming an intraclass correlation coefficient (ICC)=0.10, and two-sided type I error rate of 0.05, then we anticipate that we will have approximately 80% power to detect a difference of 1.07 standard deviations of the outcome (e.g., change in resilience score between baseline and after intervention), or the change in stigma score between baseline and after intervention) between the intervention vs. control for each of the two interventions. If ICC=0.05 (or 0.15), then we will have approximately 80% power to detect a difference of 0.85 (or 1.26) standard deviations.

For our qualitative interviews, we will continue to collect data until we have reached data saturation. Based on similar interviews conducted in 2022 (unpublished, IRB# 99/CIBS-Z/22), we believe we will reach saturation with no more than 40 interviews.

**Objective 2:** Each of the four health facility sites serve at least 4,000 patients enrolled on ART who will be scheduled for clinic visit(s) during the study period. With a minimum of  $n=4,000$  in each facility, assuming an ICC=0.05, and two-sided type I error rate of 0.05, then we anticipate that we will have approximately 80% power to detect a difference of 0.64 standard deviations of the outcome (e.g., proportion of time on medication) between the intervention vs. control. If ICC=0.025 (or 0.10), then we will have approximately 80% power to detect a difference of 0.45 (or 0.91) standard deviations.

The survey will be done in a sub-population of the cohort of HIV-positive patients at all four sites. Due to the exploratory nature, sample sizes for the patient surveys were not calculated based on existing assumptions. We estimate that 80 surveys per HF ( $n=320$ ) will provide us with the requisite baseline preliminary data on how they experience health care. For outcome

measures available on only these surveyed participants, we anticipate approximately 80% power to detect differences of 0.55, 0.71, and 0.96 standard deviations of the outcome assuming ICC of 0.025, 0.05, and 0.10, respectively.

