People living with HIV (survey): The study team will recruit participants to complete the baseline and endline surveys at the time the individuals are leaving an appointment for HIV care at one of four eligible health care facilities. Recruitment will be done using convenience sampling when the individual exits the health facility after receiving care. If the individual is interested in participating in the study, a study assistant will bring them into a private room to discuss their eligibility and study procedures (complete surveys at study baseline or endline, i.e., 6 months after the study begins, and to the use of a subset of data from their medical records regarding ART medication pick-up history within the previous 6 months). If eligible and they agree to participate, their informed consent will be obtained by the study assistant at the health facility. Participants can withdraw at any time without impact on the clinical care they are receiving.

People living with HIV who are followed as part of routine care (estimated n=16,000): The study team will not formally recruit and consent these individuals to participate in the study, as only a chart review will be performed. For the inclusion of these individuals' data, we will seek a waiver of informed consent, to be developed and included in the submission to the ethics committees/Institutional Review Board (IRB), to access their retention data and viral load results over the course of the study.

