$\text{logit}(P(Y \leq y)) = \beta_0(y) + \beta_1 \text{Intervention} + \beta_s \text{site} + \beta_x X$ , where  $\beta_1$  is the effect of the intervention on the log-odds ratio scale. Our primary objective is to test the null hypothesis,  $H_0: \beta_1 = 0$ . We will provide estimates of  $\beta_1$ , 95% Wald confidence intervals, and two-sided p-values. As with our other analyses, we will take advantage of the factorial nature of the model by grouping interventions as receiving resilience intervention (yes vs. no) and receiving anti-stigma intervention (yes vs. no). An interaction between the two interventions will also be assessed to see, for example, if the interventions are synergistic. The primary model will be adjusted for study site to acknowledge similarities between patients at the same site, and it will also be adjusted for a small number of patient-level baseline covariates, that are usually predictive of adherence to medications (e.g., age, sex, and education). In the model with the interaction between two interventions, study site will not be included so that the interaction effects are identifiable. In additional crude secondary analyses, we will investigate how changes in HCW measures correlate with patient outcomes by including average HCW metrics in models, replacing study site with this continuous variable. These latter analyses will be very much exploratory, as with only four study sites, we will have limited information to estimate these associations.

We will also compute three secondary measures of patient retention:

- (1) Monthly medication pick-up. Specifically, measured from the first day of ART initiation, any ART medication pick-up between days 16 and 45 will count as medication pick-up during month 1, any medication pick-up between days 46 and 75 will count as medication pick-up during month 2, and so forth, up until 6 months (i.e., medication pick-up between day 346 and 375); if the patient was enrolled on a three month pick up we will calculate on time pickups using the mark 15 days before and 15 days after the scheduled visit.

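### The interaction and staff-score models for time on medication make no allowance for clustering by facility, so patient-level standard errors from them cannot support inference about four facilities

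*Combined protocol and SAP*

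**What the plan says.** Section 6 (Design and Study Questions) randomizes four facilities to a control arm and three intervention arms, so each cell of the two-by-two factorial holds one facility.

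Section 10, Data Analysis, Objective 2 specifies a cumulative probability model for proportion of time on medication. The primary model is adjusted for study site, on the stated ground that patients at one site resemble each other. Two further models are treated differently:

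- **Interaction model**, meant to show whether the trainings are synergistic: "In the model with the interaction between two interventions, study site will not be included so that the interaction effects are identifiable".
- **HCW-score models**, meant to show how changes in staff measures correlate with patient outcomes: "by including average HCW metrics in models, replacing study site with this continuous variable". The text calls these crude and highly exploratory because there are only four sites.

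No clustering allowance is given for either. Wald intervals and two-sided p-values are promised for the main intervention coefficient. No separate reporting rule is given for these two models.

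Section 7.c (Calculations of Sample Size), by contrast, plans Objective 2 with clustering: "With a minimum of $n=4,000$ in each facility, assuming an ICC=0.05", with 0.025 and 0.10 as alternatives.

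**The concern.** An intercept, two main effects and their interaction use up all four facility means. Nothing is left from which to estimate how much facilities differ for reasons unrelated to training. Leaving site out makes the interaction coefficient computable, but it does not identify synergy. The coefficient remains the training interaction plus whatever the four facilities happen to contribute, and its standard error treats about 16,000 patients as independent. The HCW-score models share the problem, because a covariate with four distinct values is given the precision of a patient-level covariate.

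Hypothesis 2 concerns the site that receives both trainings, and section 12 (Limitations) says the design should show which intervention or combination does best and should inform a larger trial. A facility difference reported with a very small standard error could push that next trial towards or away from the combination, in a direction set by chance.

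**Working it through.** **Inputs.** All are from section 7.c unless noted.

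- Patients per facility, m = 4,000: "Each of the four health facility sites serve at least 4,000 patients enrolled on ART".
- Base ICC and alpha: "in each facility, assuming an ICC=0.05, and two-sided type I error rate of 0.05".
- Stated detectable differences: "approximately 80% power to detect a difference of 0.64 standard deviations of the outcome (e.g., proportion of time on medication" at ICC 0.05, and "If ICC=0.025 (or 0.10), then we will have approximately 80% power to detect a difference of 0.45 (or 0.91) standard deviations".
- One facility per cell: section 6.

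**Step 1. Reproduce the plan's figures.** Take the design effect 1 + (m − 1) × ICC, two facilities per side, and a two-sample noncentral t calculation on the effective sample size.

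| ICC | Design effect | Effective n per side (8,000 / design effect) | Detectable difference, 80% power | Stated |
|---|---|---|---|---|
| 0.025 | 100.975 | 79.2 | 0.448 SD | 0.45 SD |
| 0.05 | 200.95 | 39.8 | 0.636 SD | 0.64 SD |
| 0.10 | 400.9 | 20.0 | 0.910 SD | 0.91 SD |

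The stated figures reproduce, so the sample size section does assume this much between-facility variance.

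**Step 2. Interaction with site omitted.** Scale the total outcome variance to 1. The interaction is a contrast of four facility means (both − resilience only − anti-stigma only + control).

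- True variance: 4 × [ICC + (1 − ICC)/m].
- Variance used by the model: 4 × (1 − ICC)/m.
- Ratio: 1 + m × ICC/(1 − ICC).
- Rejection rate under a true null at two-sided 0.05: 2 × [1 − Φ(1.96/√ratio)].

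| ICC | Ratio | 1.96/√ratio | Null rejection | Model SE (SD) | True SE (SD) |
|---|---|---|---|---|---|
| 0.025 | 1 + 100/0.975 = 103.6 | 0.193 | 84.7% | 0.031 | 0.318 |
| 0.05 | 1 + 200/0.95 = 211.5 | 0.135 | 89.3% | 0.031 | 0.448 |
| 0.10 | 1 + 400/0.90 = 445.4 | 0.093 | 92.6% | 0.030 | 0.633 |

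**Step 3. Check on the planned model type.** A proportional-odds cumulative probability model was simulated with a skewed ten-level outcome, half of it at the ceiling, 1,500 runs per ICC. The outcome shape and a latent-scale ICC are assumptions. The interaction was rejected in 83.3%, 88.1% and 91.6% of null runs.

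**Step 4. HCW-score model.** With a facility score unrelated to the outcome, used alone in place of site, the same simulation rejected in 84.8%, 88.9% and 91.5% of runs. If both intervention indicators also stay in, the four facilities saturate the model and its test is numerically the interaction test.

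**Step 5. Sensitivity to ICC (assumed values below the plan's range).** Null rejection is 76% at 0.01, 38% at 0.001 and 10% at 0.0001.

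**Step 6. Can site be put back?** With intercept, both main effects, interaction and three site indicators there are seven columns of rank 4, so the interaction is not estimable. With one facility per cell there are also no degrees of freedom to estimate between-facility variance from the trial.

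**The case against.** The strongest reply is that these are side analyses in a pilot. The primary test concerns the main intervention coefficient. Section 8.a places a fully powered trial outside the study's scope, section 12 concedes that four sites are inherently limiting, and the HCW-score models carry an explicit exploratory caveat that itself names the four-site problem. This stands as an argument about severity. It does not repair the standard errors, and by its wording and position the caveat covers the HCW-score models, not the interaction.

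A reader might infer stronger claims that the documents do not support:

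- **That the plan commits to an interaction p-value.** It promises intervals and p-values explicitly only for the main intervention coefficient. Reporting them for the interaction is likely, but it is an inference.
- **That false findings will occur 85% to 93% of the time.** Those rates require a true null, a 0.05 Wald test and the planning ICCs, which are assumptions and not estimates for these facilities.
- **That the plan claims mediation.** It speaks only of correlation.
- **That all Objective 2 outcomes are affected.** Site-clustered mixed models are specified for the others, so the defect as written concerns the cumulative probability models for time on medication.
- **That nothing else distinguishes the combined site.** Four-arm summaries are planned for Objective 1, and Objective 2 is said to follow similar lines. The interaction is at most the only formal model listed for that question.

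**Conclusion.** The point holds as a should-fix. As written, both models assume zero variance between facilities. That conflicts with the ICCs in section 7.c and with the plan's own reason for adjusting the primary model for site. At 4,000 patients per facility and two-sided 0.05, the planning ICCs imply null rejection of about 85%, 89% and 93%, and standard errors roughly 10 to 21 times too small (√103.6 ≈ 10.2; √445.4 ≈ 21.1). The true size of the inflation is unknown, because the real ICC is unknown. It remains material well below the planning range, at about 38% for an assumed ICC of 0.001. No choice of variance estimator recovers a valid interaction test from one facility per cell.

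**What to change.** In section 10, Data Analysis, Objective 2:

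1. Replace the sentence that omits site for identifiability with a statement that, with one facility per arm, synergy cannot be separated from facility differences.
2. State that the four facility-level distributions of time on medication, and any interaction point estimate, will be reported descriptively and labelled as confounded with facility, with no patient-level p-value or confidence interval.
3. Optionally, add a sensitivity interval that treats the section 7.c ICCs as known. On the SD scale its half-width would be about 1.96 × 0.318 = 0.62, 1.96 × 0.448 = 0.88 and 1.96 × 0.633 = 1.24 at ICC 0.025, 0.05 and 0.10.
4. For the HCW-score analysis, show a four-point plot of facility means with no patient-level p-value or interval.

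The cost is wording only, with no change to data collection, sample size or conduct. What is lost is two inferential results that would not have been valid.

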**b. Inclusion/Exclusion Criteria:**

1. PLHIV (for medical file review)

Inclusion:

- Adult individuals, 18 years of age or older
- Active in care (i.e., not in default)
- Receiving HIV care and treatment at one of the four study sites.

2. PLHIV (for survey participation)

Inclusion:

- Adult individuals, 18 years of age or older
- Active in care (i.e., not in default)
- Receiving HIV care and treatment at one of the four study sites.
- Sought care at health facility on the day of survey data collection

Exclusion (for survey participation only):

- Any clinical or mental condition (for example, but not limited to: patients with delusions, hallucinations, impaired cognitive function, mental retardation, medical condition with physical deterioration, or under the influence of drugs or alcohol at the time of study recruitment), that as per the investigator's opinion/assessment, would preclude provision of informed consent or make study participation unsafe or unethical;
- Being at the health facility for reasons other than their own medical appointment and/or picking up their own medication;
- Those who do not have routine care at the selected health facility (e.g., individuals who receive HIV care and treatment at a different facility than their own due to stigma or other reasons).

3. Health Care Workers

Inclusion:

- Adult individuals, 18 years of age or older;
- working as physicians, nurses, medical technicians, health counselors, community health care workers, or other clinical and non-clinical staff (e.g.,

receptionists, data entry clerk) who provide health services to adults living with HIV at one of the four study sites;

- willing to be followed as a study participant during the 6-month study period, and does not intend to transfer to another HF during the study period (per investigator's assessment at time of recruitment), as self-reported.
- Be able to read and write in Portuguese, as self-reported.

Exclusion:

- Those who are not permanent members of the health facility staff (i.e., floating providers that work at multiple sites in a given week);
- Any clinical or mental condition, including influence of drugs or alcohol at the time of study recruitment, that as per the investigator's opinion/assessment, would preclude provision of informed consent or make study participation unsafe or unethical;

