- (2) Monthly medication pick-up using a “re-setting” of the ART medication pick-up timeframe for each subsequent month. Specifically, calculating next scheduled ART medication pick-up from the date of last (most recent) ART pick-up (*data to be obtained from “master card” documentation*), any ART medication pick-up between days 16 and 45 from next scheduled date will count as medication pick-up for that specific month. With each date of last (most recent) ART pick-up, the window for next scheduled medication pick-up will adjust accordingly;
- (3a) For patients on monthly medication pick up. Retention at 6 months based on Mozambique Ministry of Health (MoH) guidelines. Specifically, at days 180 and 365 if the patient has had a documented ART pick-up within 59 days of their last scheduled pick-up date (*data to be obtained from pharmacy FILA form*), then they will be considered retained at that time point. If the patient has not had a documented ART pick-up in  $\geq 60$  days from their last scheduled pick-up date, they will be considered not retained (i.e., lost to follow-up);
- (3b) For patients on a differentiated care model. Retention at 6 months will look at the most recent ART medication pick-up that occurred during the first 180 days and the date of the next scheduled pick-up falling within the 180 days or beyond; if that day falls before day 121 after initiating ART, the patient would not be considered retained at 6 months.

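### Secondary retention measures: month-6 labels carry month-12 days, two measures count from ART initiation in a cohort that includes patients already on ART, and the window in measure (2) excludes on-time pick-ups

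*Combined protocol and SAP*

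**What the plan says.** All of this is in Section 10, Data Analysis, Objective 2, in the list of secondary measures of patient retention.

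- **Measure (1), monthly pick-up.** Windows are "measured from the first day of ART initiation": days 16–45 for month 1, days 46–75 for month 2, and so on "up until 6 months (i.e., medication pick-up between day 346 and 375". Patients on three-month supply are scored differently, "using the mark 15 days before and 15 days after the scheduled visit".
- **Measure (2), monthly pick-up with re-setting.** The due date is found by "calculating next scheduled ART medication pick-up from the date of last (most recent) ART pick-up", and then "any ART medication pick-up between days 16 and 45 from next scheduled date will count as medication pick-up for that specific month".
- **Measure (3a), monthly supply.** It is headed as retention at 6 months, but is assessed "at days 180 and 365 if the patient has had a documented ART pick-up within 59 days of their last scheduled pick-up date". No day 0 is stated.
- **Measure (3b), differentiated care.** It takes the next due date after the latest pick-up in the first 180 days, and "if that day falls before day 121 after initiating ART, the patient would not be considered retained at 6 months".

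The chart-review cohort (Section 7b) is adults who are "Active in care (i.e., not in default" at one of the four sites, with no requirement of recent ART initiation. Each site has at least 4,000 patients on ART (Section 7c), and time on ART is a planned covariate for Objective 2.

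**The concern.** There are three separate problems.

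First, label and days disagree. Two measures called 6-month outcomes carry 12-month days, so a programmer who follows the days and one who follows the label produce different endpoints.

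Second, the clock starts at the wrong place for anyone already on treatment. If windows are counted from ART initiation, an established patient's months 1 to 6 are over before the training begins. Whatever is recorded there cannot respond to the intervention.

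Third, measure (2) as worded treats a patient who collects on the due date as not having collected.

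At stake is whether these secondary results can be interpreted, and whether the choices that remain open are made before or after the data are seen.

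**Working it through.** **1. Month windows in measure (1).** Inputs: month 1 = days 16–45 and month 2 = days 46–75. Each window is 30 days long and the step is 30 days, so month k = days 30k − 14 to 30k + 15.

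- k = 1: 16–45, and k = 2: 46–75. Both stated windows are reproduced.
- k = 6: 180 − 14 = 166 to 180 + 15 = 195.
- k = 12: 360 − 14 = 346 to 360 + 15 = 375, which is the window that the plan labels 6 months.
- Difference: 346 − 166 = 180 days, or six windows.

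**2. Where the windows fall for patients already on ART.** Let D be days on ART at study start (study day 0). The values of D are illustrative, because the documents give no distribution. Window k begins on study day 30k − 14 − D and ends on study day 30k + 15 − D. The day-121 cut in (3b) falls on study day 121 − D.

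| D | Month 1–6 windows wholly in the study | Study day of the day-121 cut |
|---|---|---|
| 0 | 6 | 121 |
| 90 | 3 | 31 |
| 150 | 1 | −29 |
| 180 | 0 | −59 |

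The last whole window is lost when 166 − D < 0, that is from D = 167. All overlap is lost when 195 − D < 0, that is from D = 196. If measure (1) is really meant to run to month 12, the same limits are 347 and 376 days.

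Measure (3b) does not say where its 180-day span starts. If it starts at ART initiation, the span lies wholly before the study for D of 180 or more. If it starts at study day 0 while the cut stays at ART day 121, then for D of 121 or more every due date on or after study start lies at or beyond ART day 121, and no such patient can be classed as not retained. Neither reading can show an effect of training in long-treated patients.

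**3. Measure (2), read literally.** For a 30-day supply, with the last pick-up as day 0, the due date is day 30. Days 16–45 from the due date are days 46–75 from the last pick-up. A pick-up on day 30 is not counted; only one 16–45 days late is. If days 16–45 run from the last pick-up instead, the window around the due date is 16 − 30 = −14 to 45 − 30 = +15. That is the shape of the windows in (1), so it is the likely intent for monthly supply.

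**4. Do (3a) and (3b) agree at day 180?** A due date on day 120 is 180 − 120 = 60 days overdue, and one on day 121 is 59 days overdue. The day-121 cut therefore reproduces the 59/60-day boundary of (3a), provided that both use the same day 0.

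**The case against.** The strongest reply is that these are drafting slips in secondary measures of a four-site pilot. No hypothesis test is tied specifically to them, and the primary outcome is defined separately. That is fair on importance, but it does not make the rules usable as written.

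A second reply is that counting from ART initiation is coherent if the measures are meant for new initiators. So it would be, but the plan does not say so and its eligibility criteria do not restrict the cohort. It remains open as a repair. Patients who start ART near study start, and three-month patients in (1), are not affected by the time origin.

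Several stronger readings are tempting and not supported:

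- **That the window in (2) misfires for 60-, 90- and 180-day supply.** That applies an inferred intent to supply lengths which a measure titled as monthly may not cover. What stands is that the plan should say how longer supplies are scored.
- **That the data needed do not exist.** Appendix 9 lists pick-ups for the study period only. However, the patient procedures in Section 8a describe the extraction list as not exhaustive, and Objective 2 plans a covariate on pick-ups in the previous 6 months. Earlier records can probably be obtained. For long-treated patients the fault is one of timing: with the records in hand, the outcome would still precede the intervention.
- **That 6 months is plainly the intended horizon.** The labels and the 6-month follow-up of the primary outcome point that way. Days 346–375, day 365 and routine data collection in months 1–12 point to 12 months. The documents do not settle it.

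**Conclusion.** The point holds for the secondary retention measures and should be fixed. The last window of (1) is 180 days away from its label, and (3a) has a 12-month time point under a 6-month heading. These follow from the plan's own figures and need no assumption. The literal reading of (2) excludes on-time pick-ups; that the intended window runs from the last pick-up is an inference from (1).

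The time-origin fault is certain in kind but not in extent. It removes every whole month 1–6 window from 167 days of prior ART and all overlap from 196 days, but the share of the cohort beyond those limits is not given. A reader might infer that the primary adherence analysis is compromised too. It is not: proportion of time on medication is assessed against each patient's scheduled pick-up dates over the 6-month follow-up and uses none of these windows.

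**What to change.** Before the clinical-outcome analysis in months 12–15:

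- **Day 0.** Set it for (1), (3a) and (3b) to a study start date common to all four sites, and state how patients who start ART later are handled. If ART initiation is meant, restrict these measures to new initiators and say so.
- **Measure (1).** Use days 166–195 for month 6, or relabel it as a 12-month measure.
- **Measure (3a).** Drop day 365, or name it as a separate 12-month outcome.
- **Measure (2).** For monthly supply, count a pick-up on days 16–45 from the last pick-up; successive 30-day windows then do not overlap. State whether longer supplies are scored by the existing 15-day scheduled-visit rule or excluded. Count due dates that pass without a pick-up as missed up to the 6-month horizon, stopping at death or known transfer as the primary outcome does. State how a pick-up before day 16 is treated.
- **Measure (3b).** Apply the day-121 cut in study days, so that it agrees with (3a) at day 180.

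The cost is wording and derivation code, plus one addition to the extraction: each patient's last pick-up date, scheduled date and dispensation type before study start. Appendix 9 does not list these for the full cohort, although Appendix 10 lists such records for the previous 6 months for survey participants.

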#### **Objective 2:**

With Objective 2 most of our outcomes are continuous measurements, and analyses will be similar to those described above: linear mixed effects models that take advantage of the factorial nature of outcome, with clusters defined as study sites, and unadjusted and adjusted for a small number of PLHIV-level covariates (age, sex, educational level, marital status, language, duration on ART, and history of ART medication pick-ups within the previous 6 months). For binary outcomes (e.g., undetectable viral load), we will fit generalized linear mixed effects models with a logit link function.

Every patient is given 30, 60, 90, or 180 days to pick up their ART medication, as indicated in the medical charts. If a patient picks up medication after the indicated/scheduled date, they will be considered "non-adherent" for each day after their specific pick-up date; this will be assessed over the course of the 6-month follow-up and will be treated as a continuous variable (a proportion between 0 and 1 for each participant). Participants who are lost to follow-up from the health facility during the 6-month follow-up period will be considered "non-adherent" for the days that they are lost. For persons who die or are known to have transferred care outside of the catchment area, the proportion of time on medication will be computed using only time prior to death or transfer of care. For our primary retention outcome (proportion of time on medication), normality assumptions are unlikely to hold, perhaps even after data transformation. Hence, we will fit a cumulative probability model (CPM) with fixed effects for the clinics. The CPM is well-suited for this setting because it does not require symmetry/normality in the outcome (which is bounded between 0 and 1 and likely not normal); in the absence of covariates, it reduces to the Wilcoxon rank sum test. The CPM has been shown to perform well in settings investigating medication adherence. Specifically, the distribution of the proportion of time on medication will be modeled as

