## Appendix 9: Routinely collected clinical data of all PLHIV to be extracted from EPTS (Objective 2)

1. Age
2. Sex
3. Date of HIV diagnosis
4. Education level (highest completed)
5. Marital status
6. Number of children alive
7. HIV status disclosed to family (yes/no)
8. ART initiation date
9. ART pick up dates (all during study period)
10. Scheduled ART pick up dates (all during study period)
11. Clinical appointment dates (all during study period)
12. Scheduled clinical appointment dates (all during study period)
13. Viral Load test results and dates (all during study period)
14. Pregnancy status at time of study.
15. Differentiated model of care (all documented during study period)
16. Type of drug dispensation (all documented during study period)
17. Blood pressure (all results during study period)
18. Weight (all results during study period)
19. Height
20. TB treatment
21. WHO staging
22. patient ID
23. CD4 results and dates (all during study period)

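### Secondary retention measure (1) has a schedule-based rule only for three-month supplies, so as written it credits never-late patients on 60-day and 180-day supplies with only 3 of 6 and 1 of 6 months

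*Combined protocol and SAP*

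**What the plan says.** Section 10, Objective 2, describes the dispensing schedules when it defines the primary outcome: "Every patient is given 30, 60, 90, or 180 days to pick up their ART medication, as indicated in the medical charts". The primary outcome, proportion of time on medication, then counts lateness from each patient's own scheduled date.

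Secondary retention measure (1) works differently. It uses fixed windows: "measured from the first day of ART initiation, any ART medication pick-up between days 16 and 45 will count as medication pick-up during month 1". The next step is "any medication pick-up between days 46 and 75 will count as medication pick-up during month 2, and so forth", and the series runs "up until 6 months (i.e., medication pick-up between day 346 and 375". One clause departs from these windows: "if the patient was enrolled on a three month pick up we will calculate on time pickups", taking 15 days before and after the scheduled visit as the limits.

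No clause covers 60-day or 180-day supplies. Measure (1) is not restricted to monthly patients, whereas measure (3a) is, and the separate rule for differentiated care in (3b) belongs to the third measure only. Appendix 9 lists actual pick-up dates, type of dispensation and "Scheduled ART pick up dates (all during study period" among the fields to be extracted.

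**The concern.** A patient with a 60-day or 180-day supply has no reason to come in every 30 days. If the monthly windows apply to that patient, months with no scheduled pick-up earn no credit, and a fully adherent patient looks poorly retained. The three-month clause shows that the authors saw this problem for one supply length. The remaining gap includes the longest supply, where the distortion is greatest.

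It could matter for the comparison because each arm is one facility (Sections 6 and 9) and the factorial analysis sets two sites against two. A difference in dispensing mix between sites is therefore tied to intervention assignment. The patient-level covariates listed for Objective 2 do not include supply length. History of pick-ups in the previous six months is listed but not defined, so it cannot be relied on to correct the scoring. A large number of records does not reduce a scoring bias.

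**Working it through.** **Inputs, all from Section 10, Objective 2.** Supply lengths s = 30, 60, 90, 180 days. Month 1 is days 16–45 and month 2 is days 46–75.

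**Windows.** The 30-day step gives month m = days 30m − 14 to 30m + 15.

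**The plan's own figure.** The plan labels days 346–375 as the 6-month window. By its own step, month 6 is 30×6 − 14 = 166 to 30×6 + 15 = 195, and days 346–375 are month 12 (30×12 − 14 = 346; 30×12 + 15 = 375). The label and the days need reconciling, but that is a separate matter. The proportions below are the same over 6 or 12 windows.

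**Credit for a patient who is never late.** Pick-ups fall on days s, 2s, 3s and so on. Count the monthly windows that contain one.

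| Supply | Windows credited, months 1–6 | Credit over 6 | Credit over 12 |
|---|---|---|---|
| 30 days | 1, 2, 3, 4, 5, 6 | 6/6 (100%) | 12/12 |
| 60 days | 2, 4, 6 | 3/6 (50%) | 6/12 |
| 90 days, if it had no exception | 3, 6 | 2/6 (33%) | 4/12 |
| 180 days | 6 | 1/6 (17%) | 2/12 |

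The six-window counts (6, 3, 2 and 1) were the same for every possible phase of the pick-up cycle. The result therefore does not depend on counting from ART initiation, and it also holds for patients already established on treatment.

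**Effect on a mean.** The documents give no share of patients by supply length, overall or by site. Assume identical adherence and a 10-percentage-point difference in the share on a long supply versus 30-day supply:

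- 180-day: 0.10 × (1 − 1/6) = 0.083, or 8.3 points.
- 60-day: 0.10 × (1 − 3/6) = 0.05, or 5 points.

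These apply to one site against another, or to a 10-point difference in the pooled share of two sites against two. If only one of two equal-sized sites differed, the pooled shift would be about half: 8.3/2 ≈ 4.2 and 5/2 = 2.5 points. The effect is linear in the assumed difference and is zero if the mix is the same everywhere.

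**After the repair.** With the scheduled-visit rule applied to all non-monthly supplies, the expected pick-ups in 180 days are 180/60 = 3, 180/90 = 2 and 180/180 = 1. Never-late patients score 3/3, 2/2 and 1/1.

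**The case against.** The text says which pick-ups count towards a month. It never gives a denominator or says that an empty window is a miss. The measure is titled as a monthly one, and its single clause on longer supplies suggests that such patients were meant to be judged against their own schedule. The three-month case may be an example, or the measure may be meant for monthly patients only. This has some force: the fractions are the consequence of applying the written rule, not figures that the plan states. But neither alternative is written, and either would need a change of wording.

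The reach is also limited. The primary outcome uses each patient's scheduled date, (3b) has its own rule, and no dedicated model is set out for measure (1). This stands in full.

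A third objection concerns the repair. Scoring everyone on the share of scheduled pick-ups kept would credit loss to follow-up, because a patient who stops coming generates no further scheduled dates. Take a 30-day patient who picks up at days 30 and 60 and is then lost. The monthly windows give 2/6 (33%). A share of scheduled dates gives 2/3 (67%), since only day 90 is recorded as missed. This also stands, and it is why the expected count must be fixed in advance and the 30-day scoring left alone.

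A reader might go further and infer that measure (1) shows dispensing mix instead of retention, or that the arm comparison is biased. The documents do not support that: they give no supply mix by site, and late or lost patients still lose credit under the rule.

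**Conclusion.** The point holds for one secondary measure. Followed as written, measure (1) credits patients who are never late with half of the months on a 60-day supply and one-sixth on a 180-day supply, against all of them on 30 days. The measure therefore partly reflects dispensing interval. These fractions follow from the plan's own windows and supply lengths and rest on two readings: that the monthly windows apply where no exception is written, and that a month without a pick-up earns no credit.

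The effect on the site comparison cannot be sized from the documents. The 8.3-point and 5-point shifts are conditional on an assumed 10-point imbalance with identical adherence, and are not predictions. A reader might also infer that the trial's main retention result is at risk. It is not: the primary outcome does not use this rule. The gap should be closed before analysis, so that the scoring choice cannot be seen as following the results.

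**What to change.** Amend measure (1) in Section 10, Objective 2:

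1. Keep the monthly windows for patients on a 30-day supply.
2. Extend the three-month rule, scheduled visit plus or minus 15 days, to 60-day and 180-day supplies.
3. Fix the number of expected pick-ups over six months by supply length: 3 for 60 days, 2 for 90 and 1 for 180. A patient lost to follow-up is then still counted as missing the later ones. For example, a 60-day patient who picks up at day 60 and is then lost scores 1/3, not 1/2.
4. Report the measure by supply length as well as overall.
5. State how a patient who changes supply length during follow-up is classified.

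The cost is a few sentences of wording. No new data are needed, because Appendix 9 already provides actual and scheduled pick-up dates and type of dispensation. The change affects scoring only. One small downside remains: patients on a 180-day supply contribute only about one expected event, so their score is close to all-or-nothing.
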